10.9 Access to Source Documentation

The investigators agree to allow the monitors direct access to all relevant documents, including electronic records, and the investigators will allocate their time and staff to discuss any findings or any relevant issues.

10.10 Data Generation and Analysis

All data are submitted into a quality assured database and will be reviewed by the sponsor. Data clarifications will be generated and the database will be edited as appropriate. The database will

be final when all queries have been resolved and all data management quality assurance procedures are complete. A full audit trail of all entries and changes to CRFs will be maintained in the database structure.

10.11 Retention of Data

In accordance with US federal and other national regulations, ICH, and GCP guidelines, the investigator must retain study records for at least 2 years, or as local regulations apply, after the last approval of a marketing application in an ICH region and until there are no pending or contemplated marketing applications in an ICH region or at least 2 years have elapsed since the formal discontinuation of clinical development of the investigational product. The investigator must notify the sponsor before any disposal or change in location of study records. The investigator should ensure that the location considered for archiving study records is an appropriate facility for the secure storage of study documents and records.

10.12 Financial Disclosure

Per 21 CFR 54, all investigators are required to complete a Financial Disclosure form prior to site activation, attesting to the fact that they are unaware of any financial conflicts of interest, or disclosing potential conflicts, including payments, proprietary interests and/or equity interests. Completed forms will be maintained in the Trial Master File.

10.13 Publication and Disclosure Policy

Manuscripts or abstracts for written or oral presentation by investigators associated with this study must be submitted to the sponsor at least 30 working days for approval before submission to any journal or meeting. Scientific comments by the sponsor should be taken into consideration before submission. The sponsor reserves the right to request revision of written or oral presentations or to deny such presentations if, in the opinion of the sponsor, such activity would adversely affect the drug development program.

Appendix 1 Schedule of Events

STUDY PROCEDURES	Study Visit Week ^a					
	Enrollment ^b (Day 1)	Phone calls	Week 4 (± 3 days)	Quarterly Visits (± 10 days)	End of Study or Early Termination Visit ^c	Unscheduled Visit(s) ^d
Clinic Site Visit	X		X	X	X	X
Phone Calls ^e		X				
Informed Consent	X					
I/E Criteria	X					
Physical Examination			X	X	X	X
Vital Signs			X	X	X	X
6-Minute Walk Test / Borg Dyspnea Scale ^f			X	X	X	X
WHO Functional Class			X	X	X	X
Laboratory Parameters			X	X	X	X
Pregnancy Test ^g	X		X	X	X	X
12-Lead ECG			X	X	X	X
Enrollment	X					
Study drug ^h	X	X	X	X	X	X
Drug Accountability			X	X	X	X
AE Assessment ⁱ	X	X	X	X	X	X
Conmed Assessment	X	X	X	X	X	X
Quality of life assessment	X			X ^j		
Sample collection for future research	X			X ^k		

^a Study Visits will take place at Week 4 and quarterly thereafter (i.e., Months 3, 6, 9, and 12).

^b All subjects who provide informed consent for the study and meet the eligibility criteria (Section 4.2) will be enrolled. Eligibility will be determined at the EOS Visit in the BPS-314d-MR-PAH-302 study and subjects will be enrolled in this OLE study on the same day. Data captured at the BPS-314d-MR-PAH-302 EOS Visit will be entered in the Enrollment Visit CRFs, as required by this protocol.

^c When the sponsor concludes the study or the subject withdraws consent or is terminated from the study, the subject will be required, as applicable, to return to the study site for an EOS Visit and the Study Termination CRF will be completed.

^d An Unscheduled Visit may occur at any time and involve any of the procedures listed as deemed appropriate by the investigator.

^e Phone calls: Contact with the subject should occur weekly for the first 3 weeks to ensure up-titration to the fixed dose is tolerated and assess AEs.

^f 6MWTs and Borg should be conducted each post-Enrollment Visit.

^g Pregnancy testing for females of childbearing potential. Urine test at the Enrollment Visit and serum test at all other clinic visits.

^h The initial dose in this study will be administered after enrollment. All doses administered at the study site, all dose changes, and the final dose should be recorded in subject dose administration log.

ⁱ If the subject reports or the investigator learns of any new SAE that occurs up to 30 days after the subject's last study visit, the clinical site personnel will ensure that these data are recorded on the AE CRF and the SAE Report Form completed and submitted accordingly.

^j Enrollment and Month 6 only. Patient-reported outcome of emPHasis-10 will be performed at any time during the visit.

^k At Enrollment and Month 3 in the US only. For subjects who consent, samples for future biomedical research will be collected at Enrollment (prior to initial esuberaprost dose in this study) and at Month 3 (at any point during the visit).

Appendix 2 6-Minute Walk Test Procedures

General Procedures

The administration of the 6-Minute Walk Test and specifications of the testing area should be generally consistent with the American Thoracic Society (ATS, 2002) guidelines and the usual practice of the clinical site.

To the extent possible and to lessen the opportunity for bias, test administrators should not review the subject's prior 6MWT results before conducting the test. When the 6MWT is completed the test administrator will not tell the subject the distance walked. Results of the 6MWT should not be provided to the subject during the course of the study.

The area used for the 6MWT should be pre-measured at approximately 30 meters (100 feet) in length and approximately 2 to 3 meters (7 to 10 feet) in width. There should be no turns or significant curves to the 6-minute walk area. The length should be marked with gradations to ensure the accurate measurement of the distance walked. The tester may be at the starting end of the corridor or at the midpoint of the corridor with a stop-watch. Intermittent rest periods are allowed if the subject can no longer continue. If the subject needs to rest briefly, he/she may stand or sit and then begin again when he/she is sufficiently rested but the clock will continue to run. At the end of 6 minutes, the tester will call "stop" while simultaneously stopping the watch and then measure the distance walked. At any point in the trial, if a subject is assessed for the 6MWT while using oxygen therapy, the use of oxygen should be recorded on the CRF. Oxygen use for all future 6MWTs should be conducted in accordance with the Investigator's clinical judgement.

Instructions to the Subject

Subjects should be told to wear comfortable clothing and sneakers or comfortable walking shoes. The person administering the test will use the following exact dialogue with the subject:

"The purpose of this test is to find out how far you can walk in six minutes. You will start from this point and follow the hallway to the marker (e.g., chair) at the end, turn around and walk back. When you arrive back at the starting point you will go back and forth again. You will go back and forth as many times as you can in the 6-minute period. You may stop and rest if you need to. Just remain where you are until you can go on again. However, the most important thing about the test is that you cover as much ground as you possibly can during the six minutes. I will tell you the time, and I will let you know when the 6 minutes are up. When I say STOP, please stand right where you are."

After these instructions are given to the subject, the person administering the test will then ask:

"Do you have any questions about the test?"

"Please explain to me what you are going to do."

The person administering the test will then start the test by saying the following to the subject:

“Are you ready?”

“Start when I say “GO.”

The person administering the test will tell the subject the time at 2 and 4 minutes by saying:

“You have completed 2 minutes.”

And then by saying:

“You have completed 4 minutes.”

No other instruction or encouragement will be given during the test. Eye contact with the subject should be avoided during the test.

Appendix 3 Borg Dyspnea Scale

Immediately following the 6MWT, the person administering the test will obtain a rating of dyspnea using the Borg Scale. The person will use the following dialogue:

“I would like to use the following scale to indicate the maximal shortness of breath you had during the walk test (indicate the Borg Scale). If there was no shortness of breath at all you would point to 0; if the shortness of breath was not very great you would choose from 0.5 to 2; if you were somewhat more short of breath you would select 3; and if the breathing was getting very difficult, you would choose 4 to 9, depending on just how hard it was; 10 represent the greatest shortness of breath you have ever experienced in your life. If one of the numbers does not exactly represent how short of breath you are, then you can choose a fraction between. For example, if you had shortness of breath somewhere between 4 and 5, you could choose 4 ½.”

Perceived Breathlessness (Borg Scale)

- 0 NOTHING AT ALL
- 0.5 VERY VERY SLIGHT (just noticeable)
- 1 VERY SLIGHT
- 2 SLIGHT
- 3 MODERATE
- 4 SOMEWHAT SEVERE
- 5 SEVERE
- 6
- 7 VERY SEVERE
- 8
- 9 VERY VERY SEVERE (almost maximum)
- 10 MAXIMUM

Appendix 4 WHO Functional Classification for PAH

Class I - Patients with pulmonary hypertension but without resulting limitation of physical activity. Ordinary physical activity does not cause undue dyspnea or fatigue, chest pain, or near syncope.

Class II - Patients with pulmonary hypertension resulting in slight limitation of physical activity. These patients are comfortable at rest, but ordinary physical activity causes undue dyspnea or fatigue, chest pain or near syncope.

Class III - Patients with pulmonary hypertension resulting in marked limitation of physical activity. They are comfortable at rest. Less than ordinary activity causes undue dyspnea or fatigue, chest pain, or near syncope.

Class IV - Patients with pulmonary hypertension with inability to carry out any physical activity without symptoms. These patients manifest signs of right heart failure. Dyspnea and/or fatigue may be present even at rest. Discomfort is increase by any physical activity.

Appendix 5 Adverse Events

The investigator or designee will probe each subject for any adverse events that may have occurred. When possible, always ask the same question when conducting the verbal probe in order to ensure uniformity between subjects. The subject should be asked:

“How have you been doing (feeling) since your last visit?”

“How are you doing (feeling) now?”

Based on the subject’s response to these questions, the subject should be asked additional questions relevant to any specific complaint such as:

“Have you had this symptom in the past?”

“How severe is/was the symptom?”

“How often did the symptom occur?”

“How long did the symptom last?”

“Did you take any medication to treat the symptom?”

“Did you see a physician or go to the hospital because of this symptom?”

All adverse events should be fully documented on the CRFs.

DEFINITIONS

An adverse event (AE) is defined as any untoward medical experience/occurrence associated with the use of a drug in humans, whether or not it is considered drug related. An AE may include an intercurrent illness, injury, or any other concomitant impairment of the subject’s health, as well as abnormal laboratory findings if deemed to have clinical significance. AEs may also include worsening of an existing symptom or condition or post-treatment events that occur as a result of protocol-mandated procedures.

A serious adverse event (SAE) is an AE occurring that has results in any of the following outcomes:

- Results in death
- Is life-threatening (i.e., the subject was, in the opinion of the investigator, at immediate risk of death from the event as it occurred; it does not include an event that, had it occurred in a more severe form, might have caused death)
- Requires in-patient hospitalization or prolongation of existing hospitalization
- Results in persistent or significant disability/incapacity (i.e., substantial disruption of a person’s ability to conduct normal life functions).
- Results in a congenital anomaly/birth defect in an offspring of a study subject

- Other medically significant event that, based upon appropriate medical judgment, may jeopardize the subject and may require medical or surgical intervention to prevent one of the outcomes listed above, e.g., allergic bronchospasm requiring intensive treatment in an emergency room or home, blood dyscrasias or convulsions that do not result in hospitalization, or the development of drug dependency or drug abuse.

An unexpected adverse event (UAE) is any AE not yet identified in nature, severity, or frequency in the current Clinical Investigators' Brochure or in the clinical safety updates.

Clinical Laboratory Changes: It is the investigator's responsibility to review the results of all laboratory tests as they become available. For each abnormal laboratory test result, the investigator needs to ascertain if this is a clinically significant change for that individual subject. The investigator may repeat the laboratory test or request additional tests to verify the results of the original laboratory tests. If a laboratory value is determined to be clinically significant for that subject, this is considered an AE.

INTENSITY

Adverse events will be graded on a 3-point scale and reported as indicated on the CRFs. The intensity of an AE is defined as follows:

- Mild: Discomfort noticed, but no disruption to daily activity
- Moderate: Discomfort sufficient to disrupt normal daily activity and/or requires symptomatic treatment
- Severe: Inability to work or perform normal daily activity and requires treatment

STUDY DRUG CAUSALITY

Relationship of an AE to treatment will be assessed as follows:

- **NOT RELATED:** The AE is not related if exposure to the investigational product has not occurred, OR the occurrence of the adverse event is not reasonably related in time, OR the AE is considered unlikely to be related to use of the investigational product.
- **POSSIBLE:** The AE is reasonably related in time to the administration of the investigational product AND the AE could be explained by causes other than exposure to the investigational product.
- **PROBABLE:** The AE has a plausible time relationship to the investigational product administration or use AND the investigational product is more likely than other causes to be responsible for the AE, OR is the most likely cause of the individual AE.

ACTION TAKEN

Action taken for an AE to treatment will be assessed as follows:

- Study drug dose withdrawn: Study drug administration was stopped permanently as a result of the AE.
- Study drug temporarily discontinued: Study drug administration was temporarily discontinued as a result of the AE.
- Study drug dose reduced: Study drug administration was reduced as a result of the AE.
- Study drug dose increased: Study drug administration was increased as a result of the AE.
- Study drug dose not changed: There was no alteration in either the dose or regimen of the study drug.
- Unknown: Not known what occurred with study drug administration because information is insufficient or contradictory.
- Not applicable: The subject was not on study drug at the start of the AE

OUTCOME

The outcome of an AE should be recorded based on the status of the AE at study completion or premature discontinuation from the study. The AE outcome would be recorded as fatal, not recovered/not resolved, recovered/resolved, recovered/resolved with sequelae, recovering/resolving or unknown. If an AE is ongoing, the AE should be followed until resolution.

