This study is expected to continue until the first of any of the following are reached: the study drug is commercially available, the sponsor discontinues the study, or offers enrollment in another study.

Safety Assessments:

Safety will be assessed by AEs, physical examination, vital signs, clinical laboratory parameters and electrocardiogram (ECG) findings.

Efficacy Assessments:

Efficacy will be assessed by six-minute walk distance (6MWD), the Borg Dyspnea Score, World Health Organization (WHO) Functional Class (FC), and N-terminal pro-brain natriuretic peptide (NT-pro-BNP).

Other Assessments:

Quality of life will be assessed for all subjects at Enrollment and Month 6 using the patient reported outcome (PRO) instrument, emPHasis-10.

For those subjects in the United States (US) who choose to participate and provide a separate informed consent, blood samples will be collected at Enrollment and at Month 3 (at any point during the site visit) for future biomedical research (e.g., biomarker and genomic analyses).

Statistical Methods:

The primary safety endpoint of this study is the incidence and severity of AEs associated with long-term exposure to esuberaprost in eligible subjects.

Secondary endpoints include:

- Exercise capacity as measured by unencouraged 6MWD
- Borg Dyspnea Score
- WHO FC
- NT-pro-BNP

Pertinent data will be summarized in tables, and all data will be presented in by-subject listings. No inferential analyses will be performed.

Date of Original Approved Protocol: 13 September 2017

TABLE OF CONTENTS

List of Contacts	2
Synopsis.....	3
Table of Contents	5
List of In-Text Tables	7
List of Abbreviations and Definitions of Terms.....	8
1 Introduction.....	10
2 Study Objectives.....	11
2.1 Primary Objective	11
2.2 Secondary Objective	11
2.3 Other Objectives	11
3 Investigational Plan	11
3.1 Overall Study Design and Plan.....	11
3.2 Rationale for Study Design and Control Group.....	12
3.3 Study Duration and Dates	12
4 Study Population Selection.....	12
4.1 Study Population.....	12
4.2 Inclusion Criteria	12
4.3 Exclusion Criteria	13
5 Study Treatments.....	13
5.1 Description of Treatments.....	13
5.1.1 Study Drug.....	13
5.1.2 Placebo.....	13
5.2 Treatments Administered.....	13
5.2.1 Selection and Timing of Dose for Each Patient.....	14
5.3 Method of Assigning Patients to Treatment Groups.....	14
5.4 Blinding.....	14
5.5 Unblinding Procedures.....	15
5.6 Concomitant Therapy.....	15
5.6.1 Prohibited Medications	15
5.7 Restrictions	15

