6.10.3 Severity

For each reported AE the investigator is responsible for grading its severity (or intensity) according to the criteria outlined in [Appendix 5](#) and recording these data in the subject's source documents and on the AE page of the CRF.

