9.1 General Considerations

The data collected in this study is observational and will be presented in listings and tables. No inferential statistical analyses are planned. All statistical analyses will be performed by the Sponsor's biostatistics department personnel (or appropriate designees) using SAS®, Version 9.4 or higher or other validated software.

Concomitant medications will be coded using the WHO-drug dictionary and AEs will be coded using the Medical Dictionary for Regulatory Activities (MedDRA). Coding dictionary versions will be specified in the statistical analysis plan and/or the study database.

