9.2 Determination of Sample Size

This is an open-label study for all subjects who completed the BPS-314d-MR-PAH-302 study and were eligible to continue in this study, therefore no sample size calculation was performed.

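### Appendix 5 makes the Severe grade depend on need for treatment, so an incapacitating AE that requires none can only be graded Moderate

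*Combined protocol and SAP*

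**What the plan says.** The Synopsis (Statistical Methods) sets the endpoint: "The primary safety endpoint of this study is the incidence and severity of AEs associated with long-term exposure to esuberaprost in eligible subjects". Section 6.10.3 sends the investigator to Appendix 5: the task for each AE is "grading its severity (or intensity) according to the criteria outlined in" that appendix, and the protocol gives no other severity scale.

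Appendix 5 (Intensity) states: "Adverse events will be graded on a 3-point scale and reported as indicated on the CRFs". It then sets out three grades:

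- The lowest is "Mild: Discomfort noticed, but no disruption to daily activity", which shuts out any event that gets in the way of daily life.
- The middle one is "Moderate: Discomfort sufficient to disrupt normal daily activity and/or requires symptomatic treatment", where either condition is enough.
- The top one is "Severe: Inability to work or perform normal daily activity and requires treatment", where both conditions are asked for.

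The results are descriptive. Section 9.1 says "No inferential statistical analyses are planned", and Section 9.5 promises descriptive summaries of the safety assessments, AEs among them.

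**The concern.** The Severe line asks for two different things at once: loss of function and a need for treatment. The line above it uses *and/or*, so the plain reading of *and* is that both are required. That leaves no explicit place for an AE that takes away the subject's ability to work or carry on daily life but resolves without treatment. Such events are plausible here. Section 6.10.8 lists headache, nausea, dizziness, diarrhea, fatigue and vomiting among the commonest treatment-emergent AEs, and any of these can be disabling for a short time and then pass.

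The stake is the severity table. With no hypothesis test, that table is itself the primary result for severity, and a reader will take the Severe row as the count of incapacitating events. On the literal definition it counts only those that also needed treatment.

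**Working it through.** The plan states no figure on this point to reproduce. Section 9.2 says "therefore no sample size calculation was performed", and no expected rate of Severe AEs is given. The check is therefore a reading of the three definitions against each other, followed by a simple identity for the size.

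**Inputs.** The three grade definitions and the number of grades (Appendix 5, Intensity); the instruction to use them (Section 6.10.3); the endpoint (Synopsis).

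**Step 1: classify every combination of functional impact and need for treatment.**

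| Functional impact | Treatment required? | Mild met? | Moderate met? | Severe met? | Grade on the literal text |
|---|---|---|---|---|---|
| Incapacity | Yes | No | Yes | Yes | Severe |
| Incapacity | No | No | Yes | No | **Moderate** |
| Disruption short of incapacity | Yes or no | No | Yes | No | Moderate |
| No disruption | Yes (symptomatic) | Yes | Yes | No | Mild or Moderate; the text fits both |
| No disruption | No | Yes | No | No | Mild |

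The second row is the problem. Incapacity implies disruption, so Mild is closed; no treatment is required, so Severe is closed; there is no fourth grade. Moderate is all that is left.

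**Step 2: direction.** Compare the literal rule with grading by incapacity alone. Only the second row changes, and it moves from Severe to Moderate. No row moves up into Severe. The shift at this boundary is therefore downward or zero.

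**Step 3: size.** Let N be the number of incapacitating AEs and u the share of them that require no treatment. Then

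Severe count = N − uN = (1 − u) × N.

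At u = 0 nothing changes; for any u above 0 the Severe count is lower by the fraction u. The documents give neither u nor N, so no numerical estimate follows. The total number of AEs is unchanged, because uN events leave Severe and the same uN enter Moderate.

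**Step 4: do other fields recover the lost events?** Only in part. Appendix 5 makes incapacity a seriousness criterion without any treatment condition, but only when it is persistent or significant, so a brief episode need not qualify. Seriousness is also a different attribute from the severity named in the endpoint. Concomitant medications (Section 6.11) and action taken with study drug (Appendix 5) describe how the event was handled. They do not record whether the subject was incapacitated.

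**The case against.** The best case on the other side is that this is a small wording gap with a narrow reach, and much of that stands.

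The criterion is need, not receipt. A reader might infer that any incapacitating AE that went untreated drops to Moderate, and hence that the Severe rate varies with local treatment practice. The text does not support this: an event that required treatment and did not receive it still meets Severe. The affected group is only those events that needed none.

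A reader might also count events managed by a dose change as downgraded. The protocol does not define what counts as treatment in the Severe line, so the documents do not settle that case.

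Nor can a percentage be attached. It is tempting to multiply an assumed subject incidence of Severe AEs by (1 − u), but that holds only if each affected subject has one incapacitating AE. With two independent ones, a subject loses Severe status only if both need no treatment, with probability u². At a purely illustrative u = 0.30 that is 0.30 × 0.30 = 0.09, not 0.30. The number of such events per subject is not given, and Section 3.3 sets no fixed length of follow-up.

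A net downward shift across the whole severity table is not shown either. At the lower boundary, an AE with no disruption that needs symptomatic treatment fits Moderate as well as Mild, so mixing treatment with intensity can push grades up there.

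Finally, a reader might expect the incidence of treatment-emergent AEs to fall, because Section 6.10.8 counts worsening. That would follow only if worsening were judged by change of grade, which the protocol does not say.

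What the objection does not remove is the second row of the table. On the words as written, that event cannot be graded Severe.

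**Conclusion.** The point holds in a limited form. Followed exactly, Appendix 5 sends an incapacitating AE that requires no treatment to Moderate, so the severity part of the primary safety endpoint can be understated at the Moderate/Severe boundary. The direction there is downward only. The size is unknown and may be zero: it depends on how often such events occur and on whether investigators apply *and* literally, and the documents give no figure for either. AE incidence, serious-event reporting and causality assessment are not affected, and there is no test, power calculation or decision rule to change. The documents do not support saying that esuberaprost is in fact made to look better tolerated than it is. They support saying that the scale leaves room for this and that the gap can be closed cheaply.

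**What to change.** - **Appendix 5.** Define Severe by function alone: keep the first clause of the present line, remove the treatment condition, and add *whether or not treatment is required*.
- **CRF completion guidelines (Section 10.7).** Repeat the same definition there.
- **Treatment information.** Leave it where it is already collected, under concomitant medications and action taken. Nothing is lost by removing it from the grade.
- **AEs ongoing from Study 302.** Sections 6.10.1 and 7.1 bring these into this study's CRFs, and Section 6.10.8 counts worsening as treatment-emergent. Grade them on the revised definition when they are entered at Enrollment. Otherwise a change of scale could look like a worsening.
- **Side-by-side tables.** If 302 used different wording, footnote any table that sets the two studies together.

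If the sponsor does want both conditions, Appendix 5 should say so explicitly and define treatment, and the severity table should carry a footnote that Severe excludes incapacitating events that required none.

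**Cost.** One line in Appendix 5 and matching guideline text, with the approvals that Section 10.2 requires for an amended protocol. The reported Severe count can only rise or stay the same. Comparability with 302 may suffer; these documents do not give the 302 scale, so that cost cannot be sized.
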